	13.1.2 Specification of Source Documents	
	13.1.3 Record Keeping / Archiving	
	13.2 Data Management	32
	13.3 Routine Monitoring	32
	13.4 Audits and Inspections	32
	13.5 Confidentiality, Data Protection	32
	13.6 Storage of Biological Material and Related Health Data	32
14	PUBLICATION AND DISSEMINATION POLICY	
15	FUNDING AND SUPPORT	33
	15.1 Funding	33
	15.2 Other Support	33
16	INSURANCE	33
17	REFERENCES	34
18	APPENDICES	36

STUDY SYNOPSIS

Sponsor / Sponsor- Investigator	[name]	
Study Title:	The influence of two modifiable stability boots on gait pattern in healthy adults	
Short Title / Study ID:	Stability boots	
Protocol Version and Date:	Version 3.0 of 08.03.2017	
Trial registration:	clinicaltrials.gov: NCT03038815	
Study category and Rationale	Other clinical study Category A	
Background and Rationale:	After an ankle injury like distorsions, fractures or arthrodeses, or congenital defects ankle support limit the range of motion in the joint, help pain relief, control loading of the injured tissues and promote recovery of a normal gait pattern. Gait analysis is applied in orthopedics, sport science and rehabilitation. Numerous measure systems and methods enable accurate analysis of human movement	
Objective(s):	Primary study objective: The study is set to describe and compare the gait analysis of two modifiable stability boots (Ortho® Tri-Phase and the VACOped®) on the standard walking parameters during two conditions (level and ramp walking) in healthy adults and draw comparisons with a control indoor shoe. Secondary study objectives: to analyse the whole gait pattern to examine the difficulties that occur out of ramp walking with the boots to identify differences between the modular restriction settings in both stability boots during walking	

r		
	Primary outcomes:	
	 to analyse and compare the angle of the ankle joint in the frontal and the sagittal plane 	
	to define ground reaction force outcome parameters:	
	First and second peak, minima, loading and	
0	unloading rate of the ground reaction forces	
Outcome(s):	to evaluate the COP on the sole	
	Secondary outcomes:	
	to expound biometric data: age, gender, height,	
	weight, shoe sizeto interpret time distance parameters: gait velocity,	
	stance/swing time, step and stride lengths	
Study design:	Observational study	
	Inclusion criteria:	
	healthy	
	• 18-45 years old	
	• shoe size 5,6,9 or 10	
Inclusion / Exclusion	Exclusion criteria:	
criteria:	injuries of the lower limbs	
	 previous surgeries on the lower limbs 	
	neuromuscular disorders	
	restriction in gait capabilities	
	current medical treatment Ortho® Tri Phase (stability shee)	
	Ortho® Tri-Phase (stability shoe) Gait analysis (level and ramp walking) with the Ortho® Tri-	
Study Intervention:	Phase from Künzli SwissSchuh which has three restriction	
Study intervention.	stages of Flexion/Extension (10° in the first phase and 30° in	
	the second phase and free). At least 5 gait cycles should be	
	recorded from each condition. VACOped® (stability shoe)	
,	Gait analysis (level and ramp walking) with the VACOped®	
Reference Intervention:	from OPED which has different restriction stages of	
	Flexion/Extension (-15° to 30°). Aim is to measure 3 of the	
	possible restrictions. At least 5 gait cycles should be recorded from each condition.	
Control Intervention:	Indoor shoe	
Number of Participants with	20 haalihaan artisia arta	
Rationale:	20 healthy participants	
Study Duration:	Measurements 2 months, total 6 months	
Study Schedule:	Planned start: 02.2017 Planned end: 03.2017	
	[name]	
	Institute for Biomechanics, ETH Zürich	
Investigator(s):	[name]	
mirosugator(s).	1,0000,703,000,000,000	
	[name], Switzerland	
- ,,	[contact]	
Study Centre(s):		

Statistical Considerations:	The pilot study of Bürgi & Lorenzetti 2015 was used to estimate the study sample size of 20. Significance level (α) set at 0.05 and power (1- β) at 0.8. The study will be terminated once the satisfactory power is reached with the estimated sample size. The gait analysis parameters will be described using standard descriptive statistics. Comparison between the stability boots among its outcome measures will be performed by analysis of variance tests. Significance level set at 0.05.	
GCP Statement:	This study will be conducted in compliance with the protocol, the current version of the Declaration of Helsinki, the ICH-GCP as well as all national legal and regulatory requirements.	

LIST OF ABBREVIATIONS

Adverse Event ΑE

Clinical Trial Ordinance (KlinV) ClinO

Case Report Form CRF

Electronic Case Report Form eCRF

Good Clinical Practice GCP

International Council on Harmonization ICH

Investigator Site File ISF

Institute for Biomechanics IfB

Kantonale Ethik Kommision KEK

Not applicable n.a.

Principal Investigator Ы

Range of Motion ROM

Serious Adverse Event SAE

Source Data Verification SDV

Swiss National Clinical Trial Portal SNCTP

Standard Operating Procedure SOP

Trial Master File **TMF**

STUDY SCHEDULE

Study Periods	Registration	Gait analysis
Visit	1	1
Time (hours)	30min	2 ½ -3 h
Participant Information and Informed Consent	Х	
In- /Exclusion Criteria	х	
Randomization	х	
Ortho Tri-Phase		Х
VACOped		х
Indoor shoe		х
Primary outcome measures		х
Secondary outcome measures		х

1.3 Statistician ("Biostatistician")

n.a.

2 ETHICAL AND REGULATOR ASPECTS

Before this study will be conducted, the protocol, the proposed participant information and consent form as well as other study-specific documents will be submitted to a properly constituted Competent Ethics Committee (CEC) in agreement with local legal requirements, for formal approval.

The decision of the CEC concerning the conduct of the study will be made in writing to the Sponsor-Investigator before commencement of this study. The clinical study can only begin once approval from the CEC has been received.

2.1 Study Registration

Seit November 2015 ist das Gesuchseinreichungsportal der Ethikkommissionen BASEC (Business Administration System for Ethics Committees) online. Die Gesuchseinreichungen und Publikationen müssen seither nicht mehr in SNCTP gemacht werden, sondern erfolgen direkt im BASEC. Eingereichte Informationen werden nach der Bewilligung eines klinischen Versuches von BASEC an SNCTP übergeben. (http://kofam.ch/de/studienportal/klinische-versuche-registrieren/)

The study will be registred on clinicaltrials.gov

Identifier: NCT03038815

2.2 Categorization of the Study

Category A: The health-related study intervention entails only minimal risks and burdens or is recognized as standard in guidelines prepared in accordance with internationally accepted quality criteria.

2.3 Competent Ethics Committee (CEC)

Approval from the appropriate constituted Competent Ethics Committee is sought for the clinical trial. The reporting duties and allowed time frame are respected. No substantial amendments are made to the protocol without prior CEC approval, except where necessary to eliminate apparent immediate hazards to study participants. Premature study end or interruption of the study is reported within 15 days. The regular end of the study is reported to the CEC within 90 days, the final study report shall be submitted within one year after study end. Amendments are reported according to chapter 2.9.

2.4 Ethical Conduct of the Study

The study will be carried out in accordance with principles enunciated in the current version of the Declaration of Helsinki, the guidelines of Good Clinical Practice (GCP) issued by ICH, and Swiss competent authority's requirements.

CEC will receive annual safety and interim reports and be informed about non-substantial amendments, the course of the study, and the study stop/ end in agreement with local requirements.

2.5 Declaration of Interest

There is no financing for this project planned.

2.6 Participant Information and Informed Consent

The investigator must explain to each Participant the nature of the study, its purpose, the procedures involved, the expected duration, the potential risks and benefits and any discomfort it may entail. Each participant must be informed that the participation in the study is voluntary and that he/she may withdraw from the study at any time and that withdrawal of consent will not affect his/her subsequent medical treatment.

The participant must be informed that his/her medical records may be examined by authorized individuals other than their treating physician.

All Participants for this study will be provided a participant information sheet and a consent form describing this study and providing sufficient information for participants to make an informed decision about their participation in this study.

The participant information sheet and the consent form will be submitted with the protocol for review and approval for the study by the CEC. The formal consent of a participant, using the approved consent form, must be obtained before that participant is submitted to any study procedure.

The participant should read and consider the statement before signing and dating the informed consent form, and should be given a copy of the signed document. The consent form must also be signed and dated by the investigator (or his designee) and it will be retained as part of the study records.

2.7 Participant Privacy and Confidentiality

The investigators are liable to treat the entire information related to the study and the compiled data strictly confidentially. Any passing-on of information to persons that are not directly involved in the study must be approved by the owner of the information.

Data generation, transmission, archiving and analysis of personal data within this study, strictly follows the current Swiss legal requirements for data protection. Prerequisite is the voluntary approval of the Participant given by signing the informed consent prior start of participation of the clinical trial.

Individual participant medical information obtained as a result of this study is considered confidential and disclosure to third parties is prohibited. Participant's confidentiality will be further ensured by utilizing participant identification code numbers to correspond to treatment data in the computer files.

Data generated as a result of this study are to be available for inspection on request by the monitors and by the CEC.

2.8 Early Termination of the Study

Each subject has the right to withdraw from the study at any time without prejudice. If a subject withdraws, the reason(s) will be documented

The Sponsor-Investigator may discontinue the study prematurely according to certain circumstances:

- ethical concerns.
- · insufficient participant recruitment,
- when the safety of the participants is doubtful or at risk, respectively,
- alterations in accepted clinical practice that make the continuation of a clinical trial unwise,
- early evidence of benefit or harm of the experimental intervention

2.9 Protocol Amendments

Substantial amendments (significant changes) are only implemented after approval of the CEC.

Significant changes to be authorised by the CEC are the following:

- changes affecting the participants' safety and health, or their rights and obligations;

- changes to the protocol, and in particular changes based on new scientific knowledge which concern the trial design, the method of investigation, the endpoints or the form of statistical analysis;
- a change of trial site, or conducting the clinical trial at an additional site; or
- a change of sponsor, coordinating investigator or investigator responsible at a trial site.

Under emergency circumstances, deviations from the protocol to protect the rights, safety and well-being of human participants may proceed without prior approval of the sponsor and the CEC. Such deviations shall be documented and reported to the sponsor and the CEC as soon as possible.

All Non-substantial amendments are communicated to the CEC within the Annual Safety Report (ASR).

3 INTRODUCTION

3.1 Background and Rationale

In both daily grind and sports the ankle joint is one of the most commonly injured joint in the human body (Best et al., 2011) (Morrison & Kaminski, 2007) (Van Rijn et al., 2008). In general 15% to 20% of all sporting injuries are associated with the ankle in which 75% are lesions of the ligaments. After an ankle injury like distorsions, fractures or arthrodeses, or congenital defects ankle support limit the range of motion in the joint, help pain relief, control loading of the injured tissues and promote recovery of a normal gait pattern (Kerkhoffs et al., 2002). Injuries of soft tissue like ankle ligament injuries were linked with different healing phases. First there is an inflammation phase for 1 to 5 days. Followed by the primary healing phase (5 to 28 days) with symptoms like angiogenesis, proliferating fibroblasts and collagen production. A remodelling phase terminals the rehabilitation process. The ligament stability recovers after the "form follows function" principle. The several phases are individually different in their duration and are overlapping by each other. The complete healing process last 16 to 50 weeks. Therefore, an ideal rehabilitation of an ankle ligament injury should give respect to these healing periods (Best et al., 2011). The stability boots to be tested in this thesis can be individually adapted. The modifiable ankle support has according to the healing phases different stages and restricts the joint in the two planes (frontal and sagittal) (Künzli, 2015; Oped, 2016) So far there have not been conducted gait analysis with a modifiable stability boot.

Locomotion is reproducible and follows the same physiological terms in all healthy human as it is controlled by a neuronal network known as the central pattern generator (Guertin, 2009). Gait analysis is applied in orthopedics, sport science and rehabilitation. Numerous measure systems and methods enable accurate analysis of human movement (Kramers-de Quervain et al., 2008).

When walking on levelled overground the ankle joint angle does not varying much and makes it a simple aim for orthosis and stability boot designs (Hansen et al., 2004). Human gait occurs not only on levelled ground, therefore walking uphill or downhill a ramp would be interesting to examine. Slope walking has been correlated with altering typical gait pattern of level walking of a healthy human (Gottschall et al., 2011). Kawamura et al. (1991) and Sun et al. (1996) have found that the cadence and the stride length change during hill walking. Sun et al. (1996) found that a product of a decrease in step frequency and an increase in step length account for a decreased speed in uphill walking. In comparison, during downhill walking, shorter step length due to reduction in friction was detected (Gottschall et al., 2011). Especially when walking uphill the adaptions were a result of the changes in the ankle-foot complex through plantarflexion and

dorsiflexion of the ankle (Hansen et al., 2004). Lay et al., however, did not find any significant difference in stride length between level walking and hill conditions.

The primary objective is set to describe and compare the three-dimensional kinematics and kinetics of two modifiable stability boots (Ortho® Tri-Phase and the VACOped®) on the standard walking parameters during two conditions (level and ramp walking) in healthy adults and draw comparisons with an indoor shoe.

3.2 Study Intervention and Indication

This is a study investigating healthy participants with during level and ramp walking and analysing the ankle movement with gait analysis with minimal risks to the participants.

3.3 Clinical Evidence to Date

Bürgi & Lorenzetti (2015) developed both, a machine and a fast testing method to compare prototypes of stability boots fast and objective with each other. Thus, a final prototype was developed and was tested with a gait analysis (only level walking) and compared with the already in existence standard model. The aim was to compare the stabilization effect of the final prototype stability boot with its two ankle joint restriction stages with the standard model.

Now the modified final product of this boot is in the market. The stability boot has three ankle joint restriction stages and it will be tested against the proven VACOped®.

3.4 Justification of Study Intervention

New findings could assist in further development of stability boots.

3.5 Explanation for Choice of Comparator Intervention

Comparing two stability boots.

3.6 Risk / Benefits

Risk:

No more than minimum risk for study participants. No risks are associated with measurements of ground reaction forces and skin marker positions during gait analysis. Gait analysis is a standard assessment procedure and neither physical nor psychological risks are known. The skin markers are small (1-2 cm diameter) and very light, and they do not affect the participants gait or well-being. Should a participant feel uncomfortable or exhausted, the procedure can be discontinued anytime

Benefit:

New findings could assist in further development of stability boots. The gait analysis provides exact results and new findings about gait with stability boots in daily walking conditions. Participants may have information about their gait.

3.7 Study Population

The study population consists of healthy persons between 18 and 45 years old.

4 STUDY OBJECTIVES

4.1 Overall Objective

The purpose of this project is to describe and compare the gait analysis parameters of healthy adults wearing stability boots, tracking mounted skin markers and acquiring force data using force plates.

4.2 Primary Objective

The study is set to describe and compare the three-dimensional kinematics and kinetics of two modifiable stability boots (Ortho® Tri-Phase and the VACOped®) on the standard walking parameters during two conditions (level and ramp walking) in healthy adults and draw comparisons with the control intervention; an indoor shoe.

4.3 Secondary Objectives

- to analyse the whole gait pattern
- to examine the difficulties that occur out of ramp walking with the boots
- to identify differences between the modular restriction settings in both stability boots during walking

4.4 Safety Objectives

n.a.

5 STUDY OUTCOMES

5.1 Primary Outcome

The primary outcome of this study is the difference between the stability boots and their different restriction settings during level and ramp walking.

This project is set to:

- analyse and compare the angle of the ankle joint in the frontal and the sagittal plane
- to define ground reaction force outcome parameters: First and second peak, minima,
 loading and unloading rate of the ground reaction forces
- to evaluate the COP on the sole

5.2 Secondary Outcomes

This project is set to:

to expound biometric data: age, gender, height, weight, shoe size

 to interpret time distance parameters: gait velocity, stance/swing time, step and stride lengths

5.3 Safety Outcomes

n.a.

6 STUDY DESIGN AND COURSE OF STUDY

6.1 General Study Design and Justification of the Design

An observational, open trial study will be planned. Healthy subjects will be recruited. They will be analysed during level and ramp walking with two different stability shoes and an indoor shoe.

- 20 healthy subjects will be recruited in total.
- The stability boot Ortho® Tri-Phase (Künzli SwissSchuh) will be the intervention. It has three phases of restriction of the ankle joint in the sagittal plane.
- The reference intervention will be the stability boot VACOped® (OPED AG). It has different restriction stages of Flexion/Extension (-15° to 30°).
- The control intervention will be an indoor shoe.
- The duration of the measurements will be 2 months.
 - o Planned start: 02.2017
 - o Planned end: 03.2017

Ground reaction forces: Ground reaction forces are simultaneously measured with the use of 5 force plates mounted flush in the floor and two forces plates on the ramp (Kistler, Instrumentation, Winterthur, Switzerland). The force plates are decoupled from the surrounding floor, which enables measurements of force which are undisturbed by the rolling cart. Force plate data is improved by a special correction algorithm to enhance the accuracy of the path of the centre of pressure.

Stance phase detection: Heel strike and toe off are defined based on ground reaction forces captured using the force plates.

Motion Capture: The 3D motion analysis system used is a VICON MX system (Oxfords Metrics Group, UK). It consists of 9 fixed and 3 movable MX40 motion-capture cameras with a resolution of 2352x1728 pixels and a capture frequency of 100Hz as well as of 6 fixed and 4 movable MXT160 motion-capture cameras with a resolution of 16 Megapixels and a capture frequency of 120 Hz. This adds up to 15 fixed cameras and 7 movable cameras. The instrumental error of marker position is ≤ 1mm (root mean square error).

The used marker set is based on the marker set of the University of Denver, consisting of 45 skin markers with a diameter of 14mm. This marker set will be completed by additional markers of the 53 standard marker set of the Institution for Biomechanics, ETH Zurich to a total of 62 mounted skin markers. Therefore it is based on redundant marker point clouds and functionally estimated joint centres, respectively axis (List et al., 2012)

The test procedure consists of six trials that just include the motion capture system, namely a standing trial in an anatomic upright position and a calibration motion as well as four basic motion tasks to define functional estimated joint axis, respectively centers (each performed

twice). All trials of level and ramp up and down walking are assessed simultaneously by the motion capture systems as well as force plates.

For each of the gait conditions (ramp up, ramp down and level walking) and each restriction of the stability boots (10°, 30° and 45°/free) the subjects have to perform five valid trials. In total there are at least 21*5 trials. A gait trial is considered valid, when the foot is in the field of view of the image intensifier during stance and swing phase and the force plate is hit for level and ramp gait. Mean and standard deviation of the five trials will be calculated.

Motion Tasks:

- Level walking
- Ramp up walking
- Ramp down walking

6.2 Study Duration and Study Schedule

The total duration of the study will be 6 months.

Start: 10.10.16 End: 10.04.17

Measurements: February 2017 until March 2017 Data analysis: February 2017 until April 2017

6.3 Methods of Minimizing Bias

6.3.1 Randomization

If the participant has to wear the VACOped® or the Ortho Tri-Phase® first will be randomized. Through technical reasons the indoor shoe cannot be randomized.

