7 STUDY POPULATION

7.1.1 Inclusion Criteria

Participants fulfilling all of the following inclusion criteria may be enrolled in the study:

Inclusion criteria:

- Healthy
- 18-45 years old
- shoe size 5,6,9 or 10

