7.2 Recruitment and Screening

Enrollment is planned for a period of 2 months. Direct recruitment of potential study participants, contact between the study team and potential subjects in person. Volunteers giving written informed consent will be assessed during the visit at the institute of biomechanics.

There will be no payment given as compensation for time and effort of the participants. To ensure gaining baseline data for each gender the aim is to enroll ten men and ten women.

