7.3 Assignment to Study Groups

Not applicable. Data will only be acquired in only one study group. All participants will be tested in all three interventions.

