8.5 Concomitant Intervention(s)

n.a.

STUDY PROCEDURES

This study involves one dynamic data acquisition synchronized optical motion capture with measurements of ground reaction forces during level walking and ramp walking. The expected total time involvement for each participant maximally adds up to 3 hours.

Study Flow Chart/Table of Study Procedures and Assessments 9.1

Ortho Tri-Phase with 10°, 30° and free ROM in the ankle	VACOped with 10°, 30° and 45° ROM in the ankle
level walking	level walking
ramp up	ramp up
ramp down	ramp down

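### Boot order is randomised with no requirement that the two orders be balanced, and the boot comparison has no planned period term

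*Combined protocol and SAP*

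**What the plan says.** Section 11.1 states one hypothesis, on ankle range of motion in the Ortho Tri-Phase versus the VACOped. Section 6.1 says "20 healthy subjects will be recruited in total", and 7.3 adds "All participants will be tested in all three interventions", so the boot contrast is within participant.

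The session is long. Section 6.1 says "In total there are at least 21*5 trials", and the opening of the Study Procedures section says "The expected total time involvement for each participant maximally adds up to 3 hours" (9.2.4 allows up to 4 hours).

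On order, 6.3.1 says "If the participant has to wear the VACOped® or the Ortho Tri-Phase® first will be randomized", and then "Through technical reasons the indoor shoe cannot be randomized". No section gives an allocation ratio, blocks, strata, a list or a method of generating the sequence. Section 11.3.2 compares the boots by analysis of variance without naming its terms; period, sequence and subject are not mentioned.

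Sections 7.4 and 11.4 provide for an additional subject when too many trials are invalid, but do not say which boot that person wears first. Section 7.4 also keeps the data of participants who withdraw.

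**The concern.** Section 6.3.1 implies that each participant completes one boot and then the other. Each boot takes 3 settings × 3 walking tasks × 5 valid trials = 45 trials. Fatigue, habituation to the laboratory or marker drift could make the second block differ from the first; 3.6 and 7.4 themselves foresee that a participant may become exhausted.

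If more people start in one boot than in the other, part of that block difference is added to the boot difference. As written, nothing in the design prevents an uneven split, and nothing named in the analysis would correct for one. The contrast affected is the only one for which the protocol states a hypothesis.

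**Working it through.** **Inputs from the documents.** n = 20 (6.1); both boots worn by everyone (7.3); first boot randomised, method not stated (6.3.1). The documents give no order split or block effect to reproduce. The sample-size figures in 11.2 are not needed, except that 2.7 is borrowed below as a scale.

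**Assumptions.** Order is drawn separately for each participant with probability 1/2. The block effect π (second minus first block) is common and additive, with no carry-over. Values of π = 0.5, 1 and 2 degrees are illustrations; zero is possible. The SD of the within-participant boot differences is taken as 2.7 degrees; 11.2 gives that number but not what kind of SD it is.

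**1. How uneven the split can be.** The number starting in a given boot is Binomial(20, 0.5).
- P(10/10) = C(20,10)/2^20 = 184,756/1,048,576 = 0.176, so P(unequal) = 0.824
- P(12/8 or worse) = 0.503
- P(13/7 or worse) = 0.263
- P(14/6 or worse) = 0.115

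**2. How much of the block effect enters.** Let δ be the true difference, boot A minus boot B. Participants starting in A contribute δ − π on average, and those starting in B contribute δ + π. So

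E[mean(A − B)] = δ + π × (n_B-first − n_A-first)/20.

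- 10/10: 0
- 12/8: 4/20 = 20% of π
- 13/7: 6/20 = 30% of π
- 14/6: 8/20 = 40% of π

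Over all allocations the term averages zero. The difference in group sizes has variance 20, so the root mean square share is √20/20 = 0.224. For π = 0.5, 1 and 2 degrees that is 0.11, 0.22 and 0.45 degrees.

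**3. Type I error of a paired t-test with no period term** (simulation, 40,000 replicates per cell).

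| Split | π = 0.5 | π = 1 | π = 2 |
|---|---|---|---|
| Averaged over simple randomisation | 0.049 | 0.049 | 0.049 |
| 10/10 | 0.047 | 0.037 | 0.016 |
| 13/7 | 0.054 | 0.061 | 0.072 |
| 14/6 | 0.057 | 0.078 | 0.135 |

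The 10/10 row shows that balance alone is not the whole answer. The block effect cancels from the estimate but stays in the residual variance, so the test becomes conservative.

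**4. What a period term does.** With subject and period in the model, the boot estimate is the mean of the two within-order average differences. A common π cancels at any split. The variance is (σ²/4)(1/n_A + 1/n_B), with σ the SD of differences. Relative to 10/10, where it is σ²/20, the standard error is multiplied by √[5(1/n_A + 1/n_B)]:
- 13/7: √[5 × (0.0769 + 0.1429)] = √1.099 = 1.05
- 14/6: √[5 × (0.0714 + 0.1667)] = √1.190 = 1.09

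The period term thus deals with the error from an uneven split, and balance avoids the 5 to 9% loss of precision.

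**The case against.** **The protocol does not say that order is unbalanced.** This stands. A list with ten starts in each boot fits 6.3.1 as well as a coin toss does, and every probability in step 1 depends on simple randomisation. What can be said is that balance is not required. Likewise, 11.3.2 does not exclude a period term; it names none.

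**Random order already protects the comparison.** This also stands. A reader might infer that the boot contrast is biased. It is not: over allocations the leak averages zero and type I error stays near 5%. The difficulty is conditional on the split obtained, and 13/7 or worse fails to occur about 74% of the time even under simple randomisation. But the study is run once, and an uneven split would go uncorrected under the analysis as described.

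**Sex and shoe size.** Section 7.2 says "To ensure gaining baseline data for each gender the aim is to enroll ten men and ten women" and 7.1.1 admits "shoe size 5,6,9 or 10", so a reader might infer that boot order could become confounded with sex or boot size. The documents do not support that as a threat to the planned contrast. Both characteristics are fixed within a person and cancel in the within-participant difference. With order balanced overall, imbalance within a sex matters only if the block effect differs by sex or boot differences are reported by sex. No such report is planned: 11.3.3 is marked not applicable, and the subgroups in 11.3.1 are walking task by joint restriction. The ten-and-ten figure is an aim, and the documents give no distribution of shoe size by sex.

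**Scaling against 11.2.** It is tempting to express the leak as a fraction of 18.6 − 16.5 = 2.1 degrees. That figure compares two restriction stages of a prototype, not the Ortho Tri-Phase with the VACOped, so it is not a planned boot difference.

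**Conclusion.** The point holds as a gap in specification that is worth closing; it does not invalidate the design. A draw that complies with the protocol would more often than not give unequal order groups, and the realised boot difference would then contain an unremoved share of any block effect. Whether this matters in degrees cannot be settled from the documents: at a block effect of zero nothing is lost, and at an assumed 2 degrees a 14/6 split shifts the boot difference by 0.4 × 2 = 0.8 degrees. The type I error figures rest in addition on the assumed SD of differences of 2.7. Exact cancellation, by balance or by a period term, requires a common additive block effect and no carry-over between boots.

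**What to change.** **Section 6.3.1.** State that boot order is allocated from a list prepared before recruitment in a 1:1 balanced ratio, ten participants starting in the VACOped and ten in the Ortho Tri-Phase. An additional subject recruited under 7.4 or 11.4 takes the order of the subject replaced. Balancing five and five within each sex is optional; it helps only if the block effect differs by sex or results are shown by sex, and it presumes that ten of each are enrolled.

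**Section 11.3.2.** State that the analysis of variance for the boot comparison includes subject and period (first or second boot worn). This removes a common block effect even if the final split is uneven, for example 11 versus 10 because a replaced subject's data are kept. It also stops the test being conservative when the split is even.

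**Cost.** A sentence or two in each section and a 20-line list; no further participants, visits or measurements. One degree of freedom goes to period (18 instead of 19 for error in a simple two-boot comparison of 20 people). The last allocations on a balanced list are predictable, which matters little in an open study where everyone wears both boots.
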